1.2 Background on Primary Liver Cancer

1.2.1 Epidemiology

Primary liver cancers are the third highest cause of cancer-related death globally [40]. Although incidence is lower in the UK, it is increasing, with around 4300 new cases per year at present. In England, primary liver cancers account for around 1% of all cancer cases and have a 20% survival rate at one year (Cancer Research UK Liver Cancer: Key Facts, 2014). HCC, also known as malignant hepatoma, is the most commonly occurring primary liver cancer, accounting for 45% of cases in England (National Cancer Intelligence Network: Trends in incidence of primary liver cancer subtypes), and has risk factors including hepatitis B and C and cirrhosis. Cholangiocarcinoma (CCA), cancer of the biliary tract, accounts for 40% of primary liver cancers in England and is the most common cause of death from primary liver cancer in the UK, where it has an annual mortality rate of 1500 [41].

1.2.2 Treatment Modalities

Available treatment options for primary liver cancers largely mirror those previously discussed for metastatic liver tumours, and are dependent on staging. In HCC, again resection is the gold standard for localised disease, but is not an option in cirrhosis, often the underlying cause for HCC. Consequently there is the additional option for total hepatectomy and liver transplant in cirrhosis, should a suitable donor be found. Early diagnosis and treatment of HCC can achieve survival rates of 60-70%. However, due to a lack of alternative treatment options, prognosis in advanced disease or progressive disease following local therapy is dismal [6-8]. Sorafenib has been shown to increase median survival in those with advanced HCC by almost three months over placebo in a Phase III trial of over 600 patients [42]. In the case of CCA, again surgery offers the only chance of cure, but the majority of cases are inoperable due to presence of extra-hepatic metastasis at diagnosis. A study looking at survival rates in CCA diagnosed in European adults between 1990-1999 demonstrated age-standardised five-year relative survival rate of around 12% [9]. A recent UK study has demonstrated a six-month progression free survival of 57% using combination chemotherapy [43].

1.3 Investigational Medicinal Products used in the study

1.3.1 Lyso-Thermosensitive Liposomal Doxorubicin (LTLD, ThermoDox®)

ThermoDox® (or Lyso-Thermosensitive Liposomal Doxorubicin – LTLD) is being developed within an Investigational New Drug programme in the USA by Celsion Corporation (Celsion). Celsion will provide ThermoDox® as the Investigational Medicinal Product (IMP) for this study. ThermoDox® is a liposomal drug delivery system that releases a broad-spectrum cytotoxic drug (doxorubicin) when exposed to mild hyperthermia as the trigger. Drug release occurs

in the range of 39-45°C and maximal activation of the LTSs occurs around 42°C. In this study, using FUS, we aim to achieve the desired range of mild hyperthermia for ThermoDox® release.

1.3.2 Current ThermoDox® Trials

The ongoing clinical program is currently investigating ThermoDox in two indications: hepatocellular carcinoma and recurrent chest wall breast cancer.

The lead clinical study is *A Phase III, Randomized, Double Blind, Dummy-Controlled Study of ThermoDox® (Lyso-Thermosensitive Liposomal Doxorubicin-LTLD) in Hepatocellular Carcinoma (HCC) using standardized Radiofrequency Ablation (sRFA) treatment time ≥ 45 minutes for intermediate size solitary lesions ≥ 3 cm to ≤ 7 cm.* (Celsion Protocol 104-13-302, The OPTIMA Study). This trial is designed to evaluate an optimized RFA dwell time ≥ 45 minutes based on results from the prior clinical program in HCC. The OPTIMA study was initiated in June 2014 and is designed to enroll about 550 patients. The primary endpoint is overall survival with progression free survival as a secondary endpoint.

The HEAT Study, a pivotal Phase III trial enrolled 701 newly diagnosed HCC subjects with unresectable hepatocellular carcinoma (HCC) lesions, with at least one ≥ 3.0 cm and none > 7.0 cm. The study demonstrated that ThermoDox can be safely administered in this patient population but failed to meet the primary endpoint of Progression Free Survival and Overall Survival. A *Post hoc* analysis of the data from the HEAT Study was undertaken in order to better understand the results and to identify any subgroups that may have benefited from the treatment. The analysis suggests that ThermoDox efficacy for the treatment of single lesions is greatly improved when RFA dwell time is ≥ 45 minutes which has formed the basis of the hypothesis driving the current prospective pivotal study OPTIMA.

A Phase II open label study in subjects with unresectable loco-regional recurrent breast cancer of the chest wall (RCW) administered ThermoDox in conjunction with mild local hyperthermia using microwave or ultrasound heating devices is on-going. The study has completed enrollment of 17 subjects to evaluate bioequivalence, safety and efficacy of ThermoDox manufactured at two manufacturing sites. Additionally, a Phase II open label study in subjects with RCW administering ThermoDox in conjunction with mild local hyperthermia and radiation therapy will enroll patients throughout Europe and Israel.

The most frequent adverse events in patients treated with ThermoDox® at a 50 mg/m² dose are myelosuppression (60%), haematological adverse event (related or unrelated) (45%) and alopecia (40%). Other toxicities reported in greater than 5% of patients include pyrexia, fatigue, nausea and decreased appetite. To date, no significant hypersensitivity or anaphylactoid reactions have been reported in clinical studies (refer to the ThermoDox® Investigator's Brochure [44], referred to as the 'ThermoDox® IB' from hereon).

Of particular relevance to this study, the safety profile of ThermoDox® in the HEAT study has been shown to be consistent with that of doxorubicin, with neutropenia being the most important adverse event. ThermoDox® was well tolerated with no unexpected serious adverse events.

1.4 Other research interventions

1.4.1 Mild Hyperthermia Using a HIFU Therapeutic Device

HIFU therapeutic devices employ focused ultrasound, usually through the medium of water, to provide a thermal effect, typically ablation, at a precise anatomical location (section 5.4.3). Although less commonly performed for hepatic metastatic disease than either RFA or microwave ablation, ablative HIFU has the advantage of being completely non-invasive. The University of Oxford and the Oxford University Hospitals NHS Trust have extensive clinical HIFU experience. The first extracorporeal HIFU device in Europe was used for a study performed at the Churchill Hospital between 2002 and 2004 [45]. The study used an ultrasound-guided HIFU system (Model-JC Tumour Therapy System, HIFU Technology Company Ltd, Chongqing, China) to treat 30 patients with tumour deposits in the kidney or liver, and demonstrated both safety and efficacy. This was followed by the first clinical trial of HIFU ablation of tumours in the Western world carried out in Oxford [46]. This non-randomised Phase II clinical trial compared radiological response against histological findings and again demonstrated safety and feasibility for non-invasive treatment of solid tumour deposits. These studies have led to CE-marking of the JC and JC-200 treatment devices for non-invasive treatment of solid tumours such as liver cancer, kidney tumours, breast cancer, bone tumours, pancreatic tumours and uterine fibroids.

Experiments have been performed in our laboratory using gel based tissue-mimicking model phantoms, demonstrating that the temperature rises required for release of the drug from the LTSs can be achieved using a known clinical ultrasound therapy system at a fraction of the power used for thermal ablation. The resultant bulk heating effect on the model is well below the established thresholds for thermal cell death. It follows that drug release from LTSs under mild hyperthermia is theoretically achievable without any significant thermal damage to the tissue.

In this study, using focused ultrasound (FUS) to induce mild hyperthermia in participants under controlled limits with real-time temperature monitoring, we aim to remain well below thresholds for ablation or cell death of the targeted tumour cells by thermal damage. The aim of using FUS in this study is to investigate the potential for triggered drug-release by mild hyperthermia at the targeted tumour site and not its direct ablative effect as a cancer treatment itself.

1.5 Rationale for the study

To date, purely pharmacological approaches have failed to address what is essentially a three-fold challenge: (i) to deliver therapeutically significant concentrations of active agents to the tumour vasculature while minimizing off-target effects; (ii) to release the therapeutic agent 'on-demand' at the target site; and, (iii) to improve the distribution and spread of the therapeutic agent against the intra-tumoural pressure gradient in order to achieve a therapeutically relevant concentration throughout the tumour.

1.5.1 Pre-Clinical Studies

Recent animal work performed at Oxford using ThermoDox® released using FUS has shown that increased uptake at the target site is achievable. It is proposed that this method of targeted drug delivery is clinically applicable, and may achieve increased tumour uptake and local dose for the equivalent dose of doxorubicin used in systemic chemotherapy, which has a well-established and safe toxicity profile.

1.5.2 Clinical Studies

Clinical studies have demonstrated:

1. The safety profile of ThermoDox® has been shown to be consistent with that of doxorubicin (HEAT study)
2. ThermoDox® treatment shows promise for improved progression-free survival and overall survival in the subset of HCC patients having optimal RFA (HEAT study)
3. ThermoDox® has demonstrated a dose-response effect against metastatic liver tumours [10]

If this study demonstrates successful targeted drug delivery in human subjects using ThermoDox® combined with mild-hyperthermia, this could potentially transform the future of chemotherapy in clinical practice; targeted therapy using LTSs containing other chemotherapeutic agents triggered non-invasively by mild hyperthermia could be applied to any solid tumour.

2 STUDY DESIGN

Phase 1 prospective non-randomised open label single site study to determine whether targeted release of doxorubicin from ThermoDox® ('drug') using mild hyperthermia generated non-invasively by FUS is possible in cancer patients. All participants will receive ThermoDox® and FUS.

The study will run in two parts. Part I will identify optimal FUS exposure parameters for a range of patient BMIs and tumour locations within the liver using real time thermometry data from an implanted thermometry device, such as a thermistor or thermocouple. After at least 5 participants have had the intervention using real-time thermometry, data will be reviewed by the Trial Management Group (TMG) to confirm readiness to proceed without real-time thermometry (Part II). Part II, which does not require implantation of a thermometry device, is designed to reflect how the therapy would be implemented in clinical practice. All evaluable participants from both Part I and Part II will be included in the endpoint analysis.

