To assess the safety of FUS-induced mild hyperthermia for drug delivery	1. Persistence of cell viability stain or percentage of cell or tissue necrosis under 30% following FUS exposure, as assessed by cytological or histological	1. Cytological or histological analysis of biopsy samples processed within 96hr of intervention†

	methods ¹⁶ ‡,§ 2. Adverse events deemed related to FUS up to 30 days post-intervention	2. Adverse event recording for 30 days post-intervention
To assess the local and systemic cytotoxic effects of ThermoDox® in this setting	1. Significant bone marrow suppression, deranged liver function and liver toxicity 2. Adverse events deemed related to ThermoDox® up to 30 days post-intervention	1. Grade 3 and 4 laboratory results from blood tests at Day 1 and Day 15 post intervention 2. Adverse event recording for 30 days post-intervention

Table 2: Secondary Objectives and Endpoints for Parts I & II of the TARDOX Study

Regarding participants for which doxorubicin has been released by optimal FUS exposure parameters:

Tertiary (Exploratory) Objectives	Tertiary (Exploratory) Endpoints	How and when data is captured
1. To establish the validity of other minimally-invasive and non-invasive methods of evaluating intratumoural uptake of doxorubicin as an alternative to that used in primary endpoint	Combined analysis of relevant end points to establish most effective alternative analytical method(s) for quantifying drug release	See below
a. Fluorescence microscopy of biopsy	Released biopsy samples exhibiting regions of nuclear or background fluorescence levels at least twice that of a suitable control, as assessed by fluorescence microscopy ‡,§	Microscopic analysis of biopsy samples processed within 96hr of intervention†
b. MR-Spectroscopy	Liver MRI/MR-Spectroscopy indicating ¹⁷ targeted delivery of doxorubicin to the tumour by demonstrating a statistically significant increase in the tumour:background ratio of signal intensity following intervention compared to baseline	MRI/MR-Spectroscopy signal within 36 hours of intervention
c. Plasma pharmacokinetics	A statistically significant decrease in total doxorubicin plasma levels over time-matched clearance levels, following HIFU-induced release	Analytical chemistry of plasma samples processed within 12hr of intervention†

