- A Pre-Treatment Biopsy of the tumour is taken via the co-axial needle, and used as a baseline prior to any intervention, along with the Pre-Treatment blood sample.
- A clinically approved thermometry device is then positioned through the co-axial needle to the target area and is used to obtain real-time thermometry measurements during the FUS exposure.
- The HIFU therapeutic device is aligned to the thermometry device using short test exposures of FUS.

- The tumour area is then exposed to varied and considered FUS parameters (section 5.4.3) until the thermometry confirms that the target range of mild hyperthermia has been achieved within the tumour(*).
- In addition to the FUS exposure parameters (power (watts), duty cycle, duration of treatment) and associated thermometry data, the location of tumour (liver segment) and patient BMI will be recorded for each intervention.
- The thermometry device is then replaced and a cool-down period allows the tumour to return to body temperature.
- Once the tumour has returned to normothermia, the prescribed dose of ThermoDox® is infused over a duration of 30 minutes.
- A second Unreleased Drug Biopsy of the target area is then taken via the coaxial needle (Note: ThermoDox® is circulating at this point, but not yet activated). The corresponding Unreleased Drug blood sample is also taken at this stage for pharmacokinetic analysis within 15 minutes of infusion end.
- The tumour area is then re-exposed to FUS using the exposure parameters identified earlier as being suitable to generate mild hyperthermia within the tumour. During this second FUS exposure, ThermoDox® is circulating between therapeutic and peak levels.
- After completion of the final FUS exposure, a final Released Drug biopsy is taken via the co-axial needle with the corresponding Released Drug blood sample.
- Before removing the coaxial needle, a Gelfoam® (or equivalent) plug embolization of the needle track is applied through the needle to minimise bleeding risk [47].

*Note that with increasing experience, the study team may elect to omit the step of pre-heating the tumour prior to drug delivery (1st FUS exposure) and drug infusion may be commenced shortly after alignment.

The steps of intervention of the liver tumour in Part I are summarised in Figure 4.

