The paired Pre-treatment, Unreleased and Released Drug samples (bloods and biopsies) are sent for analysis in an appropriate laboratory. Please refer to section 7 for more information on sample analysis.

[figure not shown]

Figure 4: Timeline for combination exposure of the target liver tumour in Part I (not to scale, total plasma doxorubicin PK curve is for illustrative purposes to demonstrate anticipated PK trend and is not based on actual PK data)

Part II

The optimised FUS acoustic parameters for Part I will be used in Part II. The release of doxorubicin and its therapeutic effect will be investigated. The PI or delegate will have already identified a suitable solitary target liver tumour for intervention at the Ultrasound Session (section 5.1.3.1).

Day 1 (Intervention):

- Preparation as for Part I with the exception that no real-time thermometry data acquisition or pre-intervention biopsies are required in Part II, thus the co-axial needle for biopsy can be inserted after the FUS exposure. Three peripheral blood samples for plasma analysis are taken at the corresponding stages of the intervention (Pre-treatment, Unreleased and Released) as for Part I. The time the blood and biopsy samples are taken must be noted.
- ThermoDox® is infused as per prescribed dose for a duration of 30 minutes.
- After the infusion, the lesion identified for intervention (ThermoDox® release by mild hyperthermia) is exposed to the planned FUS exposure dose, as optimised in Part I, taking into consideration the patient BMI and tumour location (section 5.4.3).
- The non-FUS control tumour, if available, is exposed to ThermoDox® alone without FUS.
- As for Part I, the FUS exposure parameters, location of tumour (liver segment) and patient BMI will be recorded for each evaluation.
- The co-axial needle is inserted and up to two ultrasound-guided Released Drug Biopsies of the tumour receiving intervention are taken, whilst the participant is still under General Anaesthetic. A biopsy is not taken of the control tumour exposed to ThermoDox® only. A corresponding Released Drug blood sample is also taken.
- Before removing the coaxial needle, a Gelfoam® (or equivalent) plug embolization of the needle track is applied through the needle to minimise bleeding risk [47].

The steps of intervention for the liver tumour in Part II are summarised in Figure 5.

[figure not shown]

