16 STATISTICAL CONSIDERATIONS

16.1 Sample size and power

Evaluable participants will be recruited to either Part I or Part II of the study, up to a maximum of 28 evaluable participants overall. Non-evaluable participants will be replaced (section 6.1).

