17.2 Subgroup analysis

No subgroup analyses are planned for the study.

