17.3 Interim Analyses

As per the study design (section 2) the TMG will review thermometry data to ascertain the point at which Part II of the study will be opened (section 18.2). Following this, there will be an interim analysis of the Part I only secondary objective, which concerns optimal FUS exposure parameters. This analysis and all other analysis will be completed at the end of the study, i.e. once recruitment is closed in Part I and Part II. Once Part II is opened, Part I of the study will also remain open and can be recruited to in parallel. During the screening process the study clinicians will consider patients for the most appropriate Part based on the availability of Part II, the tumour locations, and the present level of experience with FUS hyperthermia for tumours at similar anatomical depths and locations.

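### Pooling Parts I and II for the FUS-safety endpoints can mask how heating without thermometry performed, most clearly under the pooled 50% tissue-damage rule

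*Protocol*

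**What the plan says.** Section 2 of the protocol states that "All evaluable participants from both Part I and Part II will be included in the endpoint analysis"; section 17.1 repeats this for the final analyses. Section 17.2 reads "No subgroup analyses are planned for the study".

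Table 2 (section 3) gives the objective on the safety of FUS-induced hyperthermia two endpoints:

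- **Tissue damage:** persistence of the viability stain, or necrosis under 30%. This carries the § qualifier, so it must be shown in at least half of evaluable participants, with no distinction by Part.
- **Adverse events:** "Adverse events deemed related to FUS up to 30 days post-intervention".

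The thermometry endpoint in the same table is marked as applying to Part I only. The two FUS-safety endpoints carry no such mark.

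Section 5.4.2 describes different FUS delivery in the two Parts. In Part I the settings are varied until implanted thermometry confirms the target range, and after the infusion "The tumour area is then re-exposed to FUS using the exposure parameters identified earlier". A note lets the team drop the first heating as experience grows. For Part II, "no real-time thermometry data acquisition or pre-intervention biopsies are required in Part II"; there is one planned exposure after infusion, using settings optimised in Part I. Section 2 says Part II is designed to reflect how the therapy would be used in practice.

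Section 16.1 caps recruitment at "up to a maximum of 28 evaluable participants overall" and fixes no split. Part II may open after a review held "After at least 5 participants have had the intervention using real-time thermometry". Section 17.3 adds: "Once Part II is opened, Part I of the study will also remain open and can be recruited to in parallel".

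**The concern.** Section 1.4.1 rests its expectation of staying below damaging temperatures on controlled limits with real-time temperature monitoring. Part II removes that monitoring. Temperature is an endpoint in Part I only, so tissue damage and FUS-related adverse events are the only FUS-safety endpoints that could show overheating in Part II, and neither is separated by Part.

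A pooled figure describes a mixture of two ways of delivering FUS, in proportions the protocol does not set. It could meet the trial's own tissue-damage criterion while the version intended for practice did not. For adverse events, it could be read as giving unmonitored heating the precision of the whole trial.

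**Working it through.** The cap of 28 comes with no alpha, power, event rate or split, so there is no planned figure to reproduce. The checks below ask what pooling allows.

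**Inputs from the protocol.** At most 28 evaluable participants (16.1); at least 5 treated with thermometry before Part II can open (section 2); the 50% rule on the tissue-damage endpoint (section 3). If those five are all evaluable, Part II can hold anywhere from 0 to 23 of the 28.

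**Assumptions.** All splits and rates used below. The denominator of 28 is also a simplification. Tissue analysis is done only where biopsy mass allows, so its denominator may be smaller. Section 17.1 counts all patients for toxicity, so the adverse-event denominator may differ too.

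**1. Tissue-damage rule.** Half of 28 is 14. If every Part I participant is preserved, Part II needs max(0, 14 − n₁) preserved out of n₂ = 28 − n₁.

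| Part I / Part II | Part II preserved needed | Share of Part II |
|---|---|---|
| 5 / 23 | 9 | 39% |
| 10 / 18 | 4 | 22% |
| 14 / 14 | 0 | 0% |
| 18 / 10 | 0 | 0% |

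**2. Chance of meeting the rule.** Suppose true preservation is 95% in Part I and 40% in Part II. The pooled rule is met with probability Σₐ P(X₁ = a) · P(X₂ ≥ 14 − a), where X₁ ~ Bin(n₁, 0.95) and X₂ ~ Bin(n₂, 0.40). The comparison is P(X₂ ≥ n₂/2), Part II judged alone.

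| Part I / Part II | Pooled rule met | Part II alone reaches 50% |
|---|---|---|
| 5 / 23 | 0.57 | 0.16 |
| 10 / 18 | 0.93 | 0.26 |
| 14 / 14 | 0.997 | 0.31 |

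**3. No adverse event seen.** The one-sided exact 95% upper bound for 0/n is 1 − 0.05^(1/n).

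| n | Upper bound |
|---|---|
| 28 (pooled) | 10.1% |
| 23 | 12.2% |
| 18 | 15.3% |
| 14 | 19.3% |
| 10 | 25.9% |
| 5 | 45.1% |

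**4. Direction of masking.** With a 14/14 split and rates of 5% in Part I and 30% in Part II, the pooled rate is (14 × 0.05 + 14 × 0.30)/28 = 17.5%, which understates Part II. Exchange the rates and the pooled figure is again 17.5%, now overstating Part II's 5%. The size depends on the split: with 5% in Part I and 30% in Part II, the pooled rate is 25.5% at 5/23 and 9.5% at 23/5.

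**5. Could the Parts be compared formally?** Exact power of a two-sided 5% Fisher test was computed for 5% v 20%, 5% v 30% and 10% v 40%, over splits of 5/23, 10/18, 14/14, 18/10 and 23/5. The highest value was about 0.39. Description by Part is feasible; a test is not worthwhile.

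**6. Control tissue.** Footnote 16 allows, for tumours already necrotic at baseline, a comparison with a suitable control. Section 5.2 lists pre-treatment and unreleased biopsies for Part I but only released biopsies for Part II. A Part II tumour therefore has no pre-FUS biopsy of its own, which is a further reason not to read the two Parts' tissue results as one.

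**The case against.** The strongest reply is that safety-table layout is normally left to the statistical analysis plan, to which sections 17 and 17.5 defer and which is not among the documents reviewed. Section 17.2 says only that no subgroup analyses are planned, and a descriptive table by Part may not count as one. That stands for table layout. It does not reach the 50% rule, which the protocol itself sets on evaluable participants without separating the Parts.

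A reader might infer that by-Part analysis is forbidden and that the trial cannot say anything about the safety of unmonitored heating. The documents do not support this. Adverse events are recorded per participant (13.9), causality is judged separately for drug, FUS and biopsy (13.3), FUS settings are recorded in both Parts (5.4.2), and all clinical data are listed (19). With so few participants, each Part II event can be identified. What is missing is a pre-specified summary and conclusion for Part II.

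A reader might also infer that pooling must understate Part II risk. That is not established either. Part I usually involves an additional heating, test exposures for alignment and active variation of settings, so its event rate could be the higher one. Nor is every Part I participant heated twice.

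Finally, any contrast between Parts would be confounded. Clinicians choose the Part by tumour location and experience (17.3), some patients enter Part II because anatomy ruled out Part I (5.1.3.1), and enrolment is partly sequential. This stands, and it argues for description without a test. The Trial Management Group's review before Part II opens, and its cumulative review of adverse events, protect participants but do not change what the endpoint analysis reports.

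**Conclusion.** The point holds as a weakness in the stated analysis that should be corrected. The protocol includes both Parts in the FUS-safety endpoint analysis, plans no breakdown, and applies one 50% criterion across two ways of delivering FUS, of which the one without thermometry is meant to represent practice.

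The consequence is firmest for tissue damage: at 28 participants, any split with 14 or more in Part I lets the rule be met with no Part II participant preserved, and a 10/18 split needs only 4 of 18. For adverse events the consequence is moderate and depends on the split. The zero-event bound moves from 10.1% to 12.2% if Part II has 23 participants, and to 25.9% if it has 10.

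The bounds and the counts for the 50% rule are exact for the numbers used. The splits and the event and preservation rates are illustrations, and the direction of any difference between Parts is unknown.

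**What to change.** In Table 2 and section 17.1, pre-specify descriptive reporting of FUS-related adverse events and of the tissue-damage endpoint for Part I and Part II, each with an exact confidence interval, beside the pooled figure. Show the 50% criterion for Part II separately, and give the number of FUS exposures received by Part I participants.

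Amend section 17.2 to say that this presentation by Part is planned, and that no formal comparison of the Parts is intended because allocation is non-random and the numbers are small. State that any conclusion on the safety of FUS without thermometry will rest on Part II participants only.

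The cost is one extra table column, filled from data already collected, and a wider, less favourable safety bound for Part II than the pooled one.
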